- 2. Semi structured interviews will be carried out with a subset of participants from the intervention group and will take place after completion of the pilot study so not to impact upon outcome assessment at 6 month follow up. Semi structured interviews were chosen as the preference over focus groups for participants, and an outline interview schedule has been created (Interview schedule for mothers 21-08-2022 Vn 1.0). The interview schedule will comprise of questions for mothers from both the intervention and control groups and questions specific to each group. The interview schedule was informed by using prompts/questions which are existing benefits/implementation characteristics of similar interventions in similar populations and also developed to advise on enablers/barriers to participation to inform future research. Socio-demographic characteristics of participants will be collected at the start of the interview to establish a profile of the participants taking part in the interviews (Demographics for interview 13-02-2023 Vn 1.1). While interviews are more time consuming for the researcher, they are more convenient to the mother and allow confidentiality for the mother in the discussion and so more likely to have higher participation rates and anticipated to provide rich data in relation to the depth of understanding gained of the mothers' experiences. A previous study conducting a process evaluation with mothers and infants following a singing intervention, found low uptake in their focus groups likely due to the logistic challenges of the mother sitting and talking while having a young infant to attend to (Perkins et al., 2018). While this will still be the case for the mother regardless of method, it is planned that semi-structured interviews will be conducted face to face in person or virtually via Microsoft Teams, at a date and time convenient to the mother to allow as much flexibility as possible. Interviews will be digitally recorded via Microsoft Teams, then saved and stored securely on QUB SharePoint. If completed face to face, recording will take place using two digital voice recorders in the event of technical failure and saved and stored securely on QUB OneDrive. Transcription of audio recordings will take place as soon after data collection as possible. Transcripts will be identified by study ID only. Recordings will be destroyed after transcripts have been checked for accuracy.
- 3. Semi structured interviews will be carried out with a subset of participants from the control group and will take place after completion of the pilot study so not to impact upon outcome assessment at 6 month follow up. Interviews will be conducted, recorded and data handled and stored as described in (2). The interview schedule (Interview schedule for mothers 21-08-2022 Vn 1.0) was informed by using questions based on feasibility outcomes to gain a broader understanding of recruitment methods, attrition of mothers during study and

completion rates of outcome measures. Socio-demographic characteristics of participants will be collected at the start of the interview to establish a profile of the participants taking part in the interviews (Demographics for interview 13-02-2023 Vn 1.1).

4. A single interview will take place with the intervention facilitator/s following completion of all cycles of sessions. The interview will be conducted, recorded and data handled and stored as described in (2). The interview schedule (Interview schedule for facilitators 21-08-2022 Vn 1.0) was informed by implementation characteristics of similar interventions in similar populations. Also to allow the facilitators to provide their professional opinion on the implementation of the intervention and to advise on challenges/improvements to facilitation to inform future research.

Data analysis

- 1. Evaluation forms will enable expectations and satisfaction of the intervention to be reported on and ideas for improvement to be made.
- 2. Semi structured interviews with the intervention group will allow acceptability of the intervention to be reported on.
- 3. Semi structured interviews with the control group will allow acceptability of the research study to be reported on.
- 4. Semi structured interviews with the intervention facilitator/s will allow an understanding of the facilitators' experiences of their involvement with the intervention to be gained.

All recordings from the interviews will be transcribed verbatim by the researcher and pseudonymised transcripts will be uploaded to NVivo and analysed using an interpretive qualitative approach based on the principles of thematic analysis (Braun et al., 2014). This type of analysis focuses on identifying themes throughout the data and then be coded by identifying persistent words, phrases, experiences or concepts. Data will then be grouped according to topic, allowing further identification of sub-themes. Following coding, the data will be categorised to reflect the overall picture of the data and relationships between categories. Related categories will be merged into themes (Green and Thorogood, 2018). Reflexivity will be practiced through individual analysis conducted by the research team, then discussion and agreement. This allows any biases or assumptions about the content to be examined and for the researchers to undergo a process of self-examination (Campbell et al., 2021). These themes will be used to gain an understanding of the experiences of mothers participating in the intervention.

Ethical considerations

Ethical approval will be sought from the Faculty of Medicine, Health and Life Sciences Research Ethics Committee at QUB prior to commencing the study.

Confidentiality is paramount and will be maintained during and after the study. All information collected about participants during the course of the research will be kept strictly confidential with the exception that if they disclose information that indicates that they or someone they mention is at risk of harm, the researcher is legally obliged to pass on this information in accordance with professional guidelines. Participants are advised that all information shared within group discussions

will be treated confidentially. Any personally identifiable information entered by participants within questionnaires will be removed, anonymised or pseudonymised as appropriate.

A study advisory group will be formed, comprising of local and national professionals, paraprofessionals and parents to provide ongoing insight and expertise as the study progresses. The group will meet online at key milestones of the study, expected to be on a 6-monthly basis.

Potential risks to the study participants

Physical harm: No significant physical risks are expected to be associated with the participation in this study. A health and safety assessment of the venue for its suitability for mother and infant classes will be conducted prior to commencement of the study and on an ongoing basis during the study in accordance with QUB health and safety policy.

Psychological harm: The risk of psychological harm is expected to be minimal. Previous research using a similar intervention has shown no adverse events to study participants (Fancourt and Perkins, 2018). The intervention facilitator and assistant facilitator will be vigilant during delivery of the intervention, process evaluation interviews and during any other contacts with study participants for any sign of distress observed or verbalised by the mother. If this occurs, the researcher will take appropriate action as set out in the distress protocols for both the Mamas in Harmony sessions and interviews (Distress protocol – study 21-08-2022 Vn 1.0; Distress protocol – interview 21-08-2022 Vn 1.0).

It is acknowledged that outcome data provided at post intervention and follow up timepoints by mothers during the study would not normally be analysed until completion. However, due to completion of outcome measurement tools for anxiety and depression (EPDS and GAD-7) having the potential to identify scores above the recognised clinical threshold for the tool representing significant symptoms and/or risk to the mother and infant, these data will be analysed by the researcher within one week of receipt of the completed questionnaire from the mother. This will enable the researcher to signpost the mother to her GP and other appropriate supports as per the distress protocol (Distress protocol – study 21-08-2022 Vn 1.0). Contact will be made with the mother by the research team immediately in the event that the research team identify the mother's score as being on/above the threshold indicating the potential need for follow up care, as per the measurement tool's guidelines. A letter will be forwarded to the mother by email or post depending on preference to present to her GP providing the context for the contact (GP letter 13-02-2023 Vn 1.0). In addition to these measures, should a mother express to the intervention facilitator and/or assistant facilitator that they, their infant, or someone else may be at risk of harm, consent will be sought from the mother for the researcher to contact her health visitor and/or GP within 24 hours of disclosure to share the information. Health visitor/GP contact details will be requested directly from the mother. Safeguarding advice will be sought by the researcher from the QUB designated safeguarding officer as required.

Mothers may feel they are experiencing a level of inconvenience due to the required number of questionnaires administered. Each questionnaire will take approximately 25 minutes to complete, of which the participant will be made aware of in the participant information sheet and at the beginning of each questionnaire. Data collection at all three timepoints will take place via the Qualtrics survey platform, or by post if preferred, in order to be less intrusive to the mothers home

life and potentially be more convenient. They will be able to complete the questionnaires at a time to suit their needs and that of their infant and can be saved and returned to before submitting.

Covid 19

The researcher will be following Public Health Agency guidance regarding Covid 19 at the time of the individual stages of the intervention and follow up. The researcher will complete health and safety documentation as required to identify and reduce risk.

Benefits

The benefits to the intervention and control groups will be the opportunity to participate in research and contribute knowledge to the evidence base. The intervention group may further benefit by taking part in group based activities with their infant. All participants will receive a £15 Amazon gift card as a thank you and to acknowledge their time in taking part at the end of the study.

Dissemination

Research findings will be disseminated to audiences through academic conferences and stakeholder-related event presentations, as well as peer-reviewed academic journal publications. A study webpage will be created to disseminate progress of the study and findings to study participants and the wider public. Social media will also be used to disseminate findings to reach a wider audience and maximise impact.

The study results will be implemented to decide on progression to a definitive RCT, using data on acceptability of the intervention and recruitment and attrition rates. The process evaluation will assist in exploring the quality of implementation, potential mechanisms of change and context, allowing for the intervention and conduct of the trial to be optimised and refined as required.

Project Timetable

A Gantt chart presents the anticipated schedule of recruitment, delivery of the intervention, data collection, data analysis and dissemination (See attached).

References

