Following completion of the baseline questionnaire, participants will be randomised, with their babies, on a 2:1 allocation to the intervention (Mamas in Harmony plus usual care) and control group (usual care alone). This allocation ratio was chosen to increase data available on the intervention, owing to it being a feasibility pilot RCT. The focus is not on effect size and so, for the purposes of this study, a power calculation has not been estimated. The recruitment, baseline data collection and randomisation process will be repeated with the aim of recruiting 60 participants in total, 40 allocated to the intervention group and 20 to the control group. The sequence generation for randomisation of study participants will be carried out using a computer-generated random allocation sequence completed by a 3rd party researcher within the School of Nursing & Midwifery, QUB to test feasibility of the process for concealment of allocations from the research team. The 3rd party will inform the participant, via their preferred form of communication (email or telephone) (Dialogue from 3rd party for allocation 21-08-2022 Vn 1.0), of their allocation. They will inform those in the intervention group of the start date for the group sessions, with the aim of there being 1-2 weeks notice before sessions commence. The 3rd party will inform those in the control group that they will be contacted by the QUB researcher in 3 months for follow up data collection. The intervention group will also be provided with information giving directions and accessibility details for the venue (Directions to venue 21-08-2022 Vn 1.0). Intervention delivery will then commence. Four waves of recruitment and delivery of Mamas in Harmony are planned over an 18-month period.

During intervention delivery, the QUB researcher will send mothers a text message as a reminder for attendance the day before each weekly session (Text message reminder 21-08-2022 Vn 1.0).

All mothers in the intervention and control group will have been advised during the recruitment process that they will be contacted by the research team at approximately 3 months and 6 months post randomisation (for further data collection with questionnaires provided in the same way as the baseline assessment). The recruitment, randomisation and data collection process flow diagram is presented below:

PHASE 1: RECRUITMENT

Mothers see recruitment material and use QR code or email to contact the research team

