Further questionnaires will be administered at T2 (3 months post randomisation) (T2 questionnaire 15-01-2023 Vn 1.1) and T3 (6 months post randomisation) (T3 questionnaire 15-01-2023 Vn 1.1). All questionnaires will be administered via an electronic link in an email from the online Qualtrics survey platform and completed questionnaires saved within the Qualtrics platform. A stamped addressed envelope will be supplied to be returned to QUB, if paper copies are preferred. Paper copies will be stored securely on university premises in a locked filing cabinet accessible only by the research team behind a locked door. All data will be stored in accordance with the Data Protection legislation and will be destroyed 5 years following completion of the study.

Feasibility outcomes

The feasibility outcomes of the study will be:

- 1. The recruitment rate of study participants
- 2. Reasons for non-participation (if disclosed)
- 3. Adherence and retention of participants, including reasons (if disclosed) for attrition during the intervention.
- 4. Attrition rate of mothers at the follow up timepoints at 3 months and 6 months post randomisation
- 5. Acceptability of outcome measures for anxiety, postnatal depression, perceived stress, perceived social support, maternal postnatal attachment, health-related quality of life, and service use.
- 6. Quality of implementation, potential mechanisms of change and context

Outcome measurement

Recruitment and allocation of participants will be collected and then reported and presented in a CONSORT flow diagram (Schulz et al., 2010). Screening logs will be used by the researcher during recruitment to record numbers of mothers who agreed to participate and those who declined to participate and reason (if given) (Screening log 21-08-2022 Vn 1.0) and may be used to discover influences over recruitment and/or retention of mothers. Mothers will have the option to declare that they prefer not to say. An attendance register (Attendance register 15-01-2023 Vn 1.1) will be used at each session to gather information on mothers attendance at the group music component and social support component and if any further information was provided by mothers such as their late arrival or early departure from sessions. This will be used to establish retention of participants and adherence to the intervention.

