Attrition rates from the research study will be recorded and analysed to assess feasibility of follow up immediately post-intervention and longitudinal follow up ≥6 months in duration within a full trial. Acceptability of outcome measures will be assessed from completion rates of outcome measures, missing data and promise of effect on outcome. A standardised service use log will be provided at baseline, one to be collected at 3 months (post randomisation) (3 month service use log 15-01-2023 Vn 1.1) and one to be collected at 6 months (post randomisation) (6 month service use log 15-01-2023 Vn 1.1) to establish completion rates.

Implementation components of dose, reach, context, fidelity and challenges for intervention delivery will be reported on using data from attendance registers (dose), screening logs for discovering how mothers heard about the study (reach), semi-structured interviews during process evaluation (context, fidelity and challenges). Also use of evaluation forms (fidelity). The INNATE framework (Warran et al., 2022) used to support the design and implementation of the intervention will then be utilised following the process evaluation as a guide to attempt to identify potential causal mechanisms that may have led to an effect on outcomes.

Data analysis

Quantitative data will be analysed with descriptive statistics using SPSS version 27. Continuous data will be presented as means and standard deviations and categorical and dichotomous data presented as frequencies and percentages. Baseline comparisons between groups will be made using one-way ANOVAs, Kruskal-Wallis test and Chi-square test for linear, ordinal and categorical data respectively. Differences in (Generalised Anxiety Disorder 7 Scale) GAD-7, Edinburgh Postnatal Depression Scale (EPDS), Perceived Stress Scale (PSS), Social Support Survey (SSS), Maternal Postnatal Attachment Scale (MPAS) and EQ-5D-5L scores between groups at 3 months and 6 months (post randomisation) will be assessed using two way ANOVAs, with baseline scores included as covariates where collected. Any differences in score between groups on follow up will be of interest as evidence of promise. Mothers who dropped out versus retained at 3 months and mothers dropped out versus retained at 6 months will be reported on in terms of maternal characteristics at baseline across the two groups.

Phase 2 - Process evaluation

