- 1. Evaluation forms (Evaluation form 21/08/2022 Vn 1.0) will be administered to mothers allocated to the intervention group in person in week 8 at the end of the final session of the intervention. A box will be provided at the side of the room for mothers to place their completed forms. Mothers will be reminded that all thoughts on the intervention will be valued and used to help improve the intervention content and delivery. They will be informed that they do not have to complete the form if they do not wish to, and that the forms are anonymous. The facilitator and researcher will leave the room while mothers complete the forms. The researcher will collect the box with the completed evaluation forms after the session has closed and all mothers have departed. The forms will be used to explore expectations of and satisfaction with the intervention and ideas for improvement.

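### Does the pilot lack the data to judge follow-up immediately after the intervention, because its first follow-up questionnaire is due at about 3 months post randomisation?

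*Protocol*

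**What the plan says.** Under Outcome measurement (Phase 1), the protocol gives the recorded attrition rates a purpose: "to assess feasibility of follow up immediately post-intervention and longitudinal follow up ≥6 months in duration within a full trial".

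The times at which follow-up attrition is measured are stated elsewhere, and consistently:

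- Feasibility outcomes, item 4: "Attrition rate of mothers at the follow up timepoints at 3 months and 6 months post randomisation".
- Recruitment and randomisation: all mothers are told that they will be "contacted by the research team at approximately 3 months and 6 months post randomisation". The flow diagram shows the same two points, T2 and T3, in both arms.
- Data analysis (Phase 1): "Mothers who dropped out versus retained at 3 months and mothers dropped out versus retained at 6 months will be reported on", in terms of baseline characteristics across the two groups.

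Two other sources touch the end of the sessions. The attendance register "will be used at each session to gather information on mothers attendance at the group music component and social support component". The week 8 evaluation form goes to intervention mothers only; they are told that "they do not have to complete the form if they do not wish to, and that the forms are anonymous".

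On timing, the third party tells intervention mothers the start date "with the aim of there being 1-2 weeks notice before sessions commence".

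**The concern.** Read literally, the Outcome measurement sentence asks the attrition data to speak to a time at which nobody is followed up. No outcome questionnaire is due in either arm at session 8. The attendance register covers only the arm that has sessions, and it records attendance, not completion of outcome measures. The evaluation form is optional, anonymous and confined to the intervention arm, so it cannot be linked to a mother's follow-up status. Control mothers have no scheduled contact until 3 months.

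This could matter because follow-up attrition is a listed feasibility outcome, and the Dissemination section says the results will be used to "decide on progression to a definitive RCT, using data on acceptability of the intervention and recruitment and attrition rates". A reader might take the pilot's attrition as evidence about an end-of-intervention assessment that was never made.

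**Working it through.** The protocol gives no figure for the gap between session 8 and T2, so there is none to reproduce. It has to be derived.

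**Inputs**

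- Wait from randomisation to session 1: *w* = 1 to 2 weeks. This assumes that the aimed notice (Recruitment and randomisation) is given at randomisation. The protocol does not state the wait itself.
- Eight weekly sessions (flow diagram), so session 8 is 7 weeks after session 1, at week *w* + 7.
- T2 at 3 months and T3 at 6 months post randomisation. In calendar months, 3 months = 365.25 / 4 / 7 = 13.04 weeks and 6 months = 26.09 weeks.

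**Gap from session 8 to T2** = 13.04 − (*w* + 7)

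- *w* = 1: 13.04 − 8 = 5.04 weeks
- *w* = 2: 13.04 − 9 = 4.04 weeks

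**Other ways of counting**

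| 3 months taken as | End of intervention | *w* = 1 | *w* = 2 | Wait at which the gap is zero |
|---|---|---|---|---|
| 13.04 weeks | session 8 (*w* + 7) | 5.04 | 4.04 | 6.04 |
| 13.04 weeks | full 8 weeks (*w* + 8) | 4.04 | 3.04 | 5.04 |
| 12 weeks | session 8 (*w* + 7) | 4 | 3 | 5 |
| 12 weeks | full 8 weeks (*w* + 8) | 3 | 2 | 4 |

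With a wait of 1 to 2 weeks the gap is therefore 2 to 5 weeks. It closes if the wait reaches about 4 to 6 weeks.

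**Gap from session 8 to T3** in calendar months: 26.09 − 8 = 18.09 weeks and 26.09 − 9 = 17.09 weeks.

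**How firm is the wait?** Recruitment runs in waves, with 10 to 12 dyads per group. At 2:1 allocation, a group that size needs 10 × 3/2 = 15 to 12 × 3/2 = 18 mothers randomised. Mothers are randomised after completing the baseline questionnaire, so one who completes it early in a wave could wait longer than 2 weeks, and her T2 would then fall nearer to session 8. T2 is itself only approximately at 3 months.

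**What would differ under tighter wording?** Four things depend on attrition: the two questionnaire dates, the attrition rates at those dates, the comparison of mothers who dropped out with those retained, and the progression decision. Each is defined without reference to an immediate assessment. None would change.

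**The case for a change.** The strongest case for acting is that the protocol contradicts itself on what its visits can show. On the aimed timetable T2 comes about a month after the last session, and it is counted from randomisation, not from session 8. No other source fills the gap in both arms. This is not a detail left to an analysis plan, and correcting it would cost a few words.

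The facts in that case stand: T2 is not immediate on the aimed timetable, and attrition at session 8 is not observed. The inference that the plan needs changing does not follow, for three reasons.

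- The sentence concerns what a full trial could do. Using attrition at the first questionnaire after the sessions to judge a later trial's post-intervention follow-up is ordinary extrapolation from a pilot. The same sentence speaks of follow-up of 6 months or longer, although the pilot stops at 6 months. Both halves can be read as projections.
- The section on potential risks to participants refers to a post-intervention and a follow-up timepoint, and then to three data collection points in all. With baseline, T2 and T3 the only three, the natural reading is that T2 is the post-intervention point. The two halves of the sentence then match T2 and T3.
- The progression statement in Dissemination refers to attrition rates in general. It does not rest on an immediate follow-up.

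The forward-looking reading is not spelled out in the protocol, so the wording remains looser than it should be.

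**Conclusion.** One adverb is loose; the design is not at fault. On the aimed timetable T2 falls about 4 to 5 weeks after session 8, or 2 to 5 weeks across the ways of counting. This rests on sessions starting 1 to 2 weeks after randomisation, and the gap is smaller where the wait is longer. The study can describe follow-up at 3 and 6 months post randomisation, and that is what its outcome list and analysis section say it will report.

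An analyst following the protocol would report attrition at T2 and T3, labelled by time since randomisation, and would have no session 8 rate to misreport. A definitive-trial team wanting an assessment right at the end of the sessions would see from the schedule that the pilot's nearest evidence is T2. Rewording would alter no visit, estimate or decision, so no change is called for.

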A systematic review conducted in 2016 of observational studies, including 221,974 women across 34 countries, showed prevalence of anxiety symptoms as 22.9% across the three trimesters of pregnancy, and 17.8% in the first 4 weeks following childbirth, decreasing only slightly to 15% thereafter (Dennis et al., 2017). Overall findings from the review showed a significantly higher rate of anxiety among the maternal population compared to the adult population in general. No differences in prevalence rates were found between studies published before 2010 compared to those published afterwards (Dennis et al., 2017), indicating that perinatal anxiety is an ongoing concern.

Associations between maternal anxiety and decreased coping strategies (George et al., 2013) and increased rates of suicide have been found (Farias et al., 2013). Studies investigating the effect of poor postnatal mental health have found an adverse impact on mother-infant attachment (McMahon et al., 2006), bonding, self-regulation and empathy (Rossen et al., 2016). Consequently, mothers find it difficult to engage with their infants both emotionally and behaviourally resulting in reducing their physical contact (Holt et al., 2021). Provision by the mother of a less stimulating environment, being less attuned to their infant (Brummelte and Galea, 2016) and reduced competence and low mood in the mother (Beebe et al., 2011) are also reported effects.

Poor child development outcomes in the longer term, involving behavioural and emotional problems in children aged 4 years (O'CONNOR et al., 2002) and attention deficit hyperactivity disorder symptoms at age 8-9, were also shown when mothers experienced high levels of maternal anxiety (Van den Bergh and Marcoen, 2004). Children of mothers with postnatal depression were more likely to be underweight and have poor social, emotional and cognitive development (Yang et al., 2019). Long lasting significant effects on the mother can occur if mental health issues are left untreated (Bauer et al., 2014).

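### EPDS and GAD-7 are scored early because they may signal risk, yet the protocol permits up to a week from receipt before scoring; one working day is practicable.

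*Protocol*

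**What the plan says.** All of the rule stands in the Protocol, Potential risks to the study participants, in the text on psychological harm.

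- **Reason for early review.** Outcome data would normally wait until the study ends. The EPDS and GAD-7 are an exception because they can show scores "representing significant symptoms and/or risk to the mother and infant".
- **Time limit.** For that reason "these data will be analysed by the researcher within one week of receipt of the completed questionnaire from the mother".
- **Action.** "Contact will be made with the mother by the research team immediately" once the team has identified a score that reaches the instrument's cut-off. The mother is pointed to her GP and other support under the distress protocol, and is sent a letter to take to the GP.
- **Spoken disclosure.** If a mother tells the facilitator or assistant that someone may be at risk of harm, a separate rule applies: with her consent, her health visitor or GP is contacted within 24 hours.
- **Route of the forms.** "Data collection at all three timepoints will take place via the Qualtrics survey platform, or by post if preferred".

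Under Recruitment and randomisation, the study proceeds "with the aim of recruiting 60 participants in total, 40 allocated to the intervention group and 20 to the control group", and "Four waves of recruitment and delivery of Mamas in Harmony are planned over an 18-month period". Control mothers are told that "they will be contacted by the QUB researcher in 3 months for follow up data collection".

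**The concern.** The early review exists because a score may point to risk. The step that reveals the risk carries a one-week limit, and the urgent step is timed only from the result of the first. The word immediately therefore sets no limit on the interval from the mother submitting her answers to someone reading them. For a paper form, postal transit comes on top, because the week runs from receipt.

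What is at stake is participant safety. The interval delays the referral advice and the GP letter that the step is there to trigger. The matter is somewhat sharper for control mothers, who have no planned study contact between allocation and the 3-month questionnaire, so that form may be the study's first signal from them. Estimates, power and error rates are not involved.

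**Working it through.** The one-week limit is an operational rule, so there is no derived figure to reproduce. The check is a reading of the clock, followed by simple counts.

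**1. Longest wait as written.** Receipt to scoring: 0 to 7 days. Scoring to contact: about 0 days (immediate). Receipt to contact: 0 to 7 days. Postal transit is extra and is not stated.

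**2. Longest wait to scoring with a one-working-day limit.**

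| Form received | Scored by | Longest wait | Shorter than 7 days by |
|---|---|---|---|
| Most weekdays | next day | 1 day | 7 − 1 = 6 |
| Friday | Monday | 3 days | 7 − 3 = 4 |
| Friday before a Monday holiday | Tuesday | 4 days | 7 − 4 = 3 |

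Longer closures save less. A clause capping the wait at one week ensures that the new rule is never slower than the present one. Postal transit is unchanged.

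**3. Workload.** Inputs: 60 mothers, two follow-up questionnaires, four waves, 18 months (Recruitment and randomisation).

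- Follow-up forms: 60 × 2 = 120 at most.
- With baseline: 60 × 3 = 180 at most. This is conditional. The early-review text speaks of the post-intervention and follow-up timepoints, and the Phase 1 data analysis section refers to baseline scores only where they were collected.
- Average: 180 / 18 = 10 a month at most.
- Clustering: 60 / 4 = 15 forms per wave and timepoint.

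**4. Illustration of how many scores might need action.** The protocol's opening background gives the prevalence of postnatal anxiety symptoms as "17.8% in the first 4 weeks following childbirth, decreasing only slightly to 15% thereafter". Assume that every form is returned and that this prevalence equals the share of GAD-7 scores reaching the cut-off.

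- Follow-up: 0.15 × 120 = 18.
- Baseline: from 0.15 × 60 = 9 to 0.178 × 60 = 10.7.
- All three timepoints: 18 + 9 = 27 to 18 + 10.7 = 28.7.

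These are forms, not distinct mothers, and not mothers actually delayed. The true share may differ. The protocol gives no comparable EPDS figure, so EPDS flags are not counted. The conclusion does not depend on this step.

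**The case against.** The strongest reply is that nothing here is an error. No standard in the protocol is breached by one week, and early review already goes beyond what the protocol describes as normal practice. The limit permits same-day scoring, so the real saving could be nil. The handling of distress is referred to a separate distress protocol that was not available for this review and may be faster. The action is referral advice, not emergency response. Severe mental illness is an exclusion, both arms keep midwife, GP and health visitor care, and psychological risk is expected to be minimal.

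Much of this stands, and it keeps the point small. It does not remove it. One week is the only commitment on scoring time that the protocol makes, and a safety step should be judged by what it allows. If the distress protocol is faster, the change merely brings the two into line.

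Two practical objections also stand. The protocol describes Qualtrics as delivering and storing questionnaires, not as scoring them or sending alerts, so automatic flagging cannot be presumed. An automatic flag arriving at night or at a weekend could also trigger the duty of immediate contact when nobody is at work. The fix must deal with both.

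A reader might infer that the plan contradicts itself, because 7 days is seven times the 24 hours allowed after a spoken disclosure. The text does not support that: the 24-hour rule has a different trigger, an explicit statement of possible harm, while a score reaching the cut-off indicates only that follow-up care may be needed. A reader might also infer that control mothers go unobserved for 3 months. They keep usual care, and staff are asked to watch for distress in any contact with participants.

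**Conclusion.** The point holds as a cheap safety improvement, not as a mistake in the plan. The protocol permits up to 7 days from receipt to scoring of two scales that it singles out because they may reveal risk, and nothing in the text shown shortens that. A one-working-day limit would lower the ceiling by 6 days on most weekdays, 4 over an ordinary weekend and 3 before a Monday holiday, for at most 120 to 180 forms.

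This rests on reading the limit as a maximum and on the distress protocol not already setting a shorter one. It would be wrong to conclude that mothers will wait a week: the protocol gives no expected delay.

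**What to change.** In the sentence on early review, replace the one-week limit with: within one working day of receipt, and never more than one week. In addition:

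- Apply the same limit to online and paper forms, at every timepoint at which the two scales are completed.
- State that immediate contact means the same working day on which the score is identified. This also settles flags that arrive out of hours.
- Name an existing team member to score forms when the researcher is absent.
- Align the distress protocol, and the participant information sheet if it states the limit.
- Treat automatic scoring or flagging in Qualtrics as optional, if the set-up supports it. Otherwise score by hand within the same limit.

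Leave the questionnaire order, the cut-offs and the 24-hour disclosure rule as they are.

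The cost is a small change of text in two or three documents. The downside is that forms are handled as they arrive, in clusters of about 15 per wave and timepoint, instead of in a weekly batch, and absence cover has to be arranged within the team.
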